33. Drugs or Devices.....	16
Checklist Section	16

1. Objectives

- 1.1. To determine whether the use of a balanced-salt / physiologic level of Cl⁻ crystalloid solution (Isolyte) as compared to NS in cardiac surgery leads to less kidney injury as measured by the composite [TIMP-2]*[IGFBP7] bioassay.

2. Background

- 2.1. Acute kidney injury (AKI) is a potential complication for patients undergoing cardiac surgery. AKI in post-cardiac surgery patients is associated with adverse outcomes, such as prolonged intensive care and hospital stay, diminished quality of life, increased long-term mortality, and an increased risk of chronic kidney disease requiring dialysis.[1-4] The mortality in cardiac surgery patients with AKI severe enough to require renal replacement therapy (RRT) can be as high as 60%.[5]

There are a number of causes and risk factors associated with AKI including poor preoperative cardiac function, diabetes, peripheral vascular disease, and female gender.[6] One of the putative agents associated with AKI in animal models receiving crystalloid fluids for resuscitative interventions is excess exogenous chloride ion (Cl⁻).[7, 8] As compared to non-Cl⁻ containing solutions in animal models, excess Cl⁻ appears to lead to a hyperchloremic metabolic acidosis, increased renal vascular resistance, reduced renal blood flow, and reduced glomerular filtration rate – all of which are injurious to kidney function.[9-11]

In non-cardiac surgery, including kidney transplantation, the use of low-chloride containing crystalloids leads to less acid-base and electrolyte perturbation.[12, 13] In trauma resuscitation, low Cl⁻ containing resuscitation solutions are also associated with more ideal acid-base status.[14]

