- 3.1. This is a prospective, open-label, randomized, single center, controlled clinical study to determine the effect of intraoperative infusion of NS versus Isolyte on post-cardiac surgery on AKI event (renal injury) as measured by urinary [TIMP-2]*[IGFBP7] levels. After informed consent, we will randomly assign 30 trial-completing participants (potentially enrolling up to 40 to account for any dropouts) to the two study arms in a 1:1 ratio. We will compare the effect of electrolyte solution on patients' post- vs. preoperative [TIMP-2]*[IGFBP7] score differences with pairwise t-tests, and will similarly analyze routine demographic data and potential confounders, as well as secondary outcomes as listed below.
- 3.2. This is an open-label trial.

4. Inclusion and Exclusion Criteria

- 4.1. Participants will be drawn from the population of adult patients undergoing cardiac surgery at UNMH.

The Impact of Low Chloride Containing Fluids on Acute Kidney Injury after Cardiopulmonary Bypass as Assayed by Urinary [TIMP2]*[IGFBP7]

- 4.2. Inclusion criteria: consenting adult male and female patients undergoing non-emergent on- and off-pump cardiac surgery including: bypass grafting, valvular procedures, congenital defect correction, and thoracic aortic procedures or a combination of these procedures.

Exclusion criteria: emergency surgery, pregnancy, previous renal transplantation, documented moderate to severe AKI prior to enrollment (e.g. RIFLE-I or RIFLE-F/KDIGO stage 2 or 3), patients already receiving dialysis (acute or chronic) or in imminent need of dialysis at time of enrollment, subjects with chronic kidney disease without baseline serum creatinine value (baseline within 6 months of enrollment).

- 4.3. This study does not involve adults unable to consent, individuals who are not yet adults, pregnant women, or prisoners.
- 4.4. We will not exclude particular populations such as women, children, persons not fluent in English, any particular racial or ethnic groups, etc.

5. Number of Subjects

- 5.1. This is not a multicenter study; all recruitment will occur at UNMH.
- 5.2. We plan to recruit sufficient participants to obtain complete data on 30 subjects (15/group). We do not anticipate a high withdrawal rate, but may recruit as many as 40 to have a complete dataset of this size. Recruitment will stop upon attainment of the full sample of 30, or with the 40th consenting patient who at least begins study treatment (whichever comes first).

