- 5.3. A power analysis with G*Power 3.1.9.2 software indicates that n=30 is sufficient in the context of a t-test to detect a difference between groups for the primary outcome that is roughly equal to the sample standard deviation. For (purely hypothetical) example, if the mean is 100 units and roughly 2/3 of the sample falls between 95 and 105, we would have 80% power to detect a treatment difference of 5 units.

6. Study Timelines

- 6.1. All data collection will occur in conjunction with clinically-indicated surgical care. The existence of this study will not affect the decision to refer for surgery, or the subsequent decision to proceed or not proceed with surgery, for any patient.
 - Data collection will include pre-operative serum creatinine levels, which are very likely to already have been recorded for clinical reasons. The maximum pre-operative interval for this value will be six months (it is extremely unlikely that sufficiently recent serum creatinine data will be unavailable, but if this is the case, this value will be obtained prior to surgery). Other data will be gathered immediately prior to surgery, immediately after surgery, and up to 48 hours postoperatively. It is anticipated that all participants will already be in the hospital for all data collection.
 - A recruitment period duration of one year should be sufficient to recruit the targeted participant sample; we will apply for continuing review prior to study expiration if the target sample size is not met at that time.

The Impact of Low Chloride Containing Fluids on Acute Kidney Injury after Cardiopulmonary Bypass as Assayed by Urinary [TIMP2]*[IGFBP7]

- Upon completion of data collection, the investigators anticipate one year for completion of all analyses, manuscript/presentation preparation, and submission of scholarly product to relevant outlets.

7. Study Endpoints

7.1. The primary outcome is the change in urinary [TIMP2]*[IGFBP7] composite from baseline to 24 hours postoperatively.

The secondary outcomes are:

- serum creatinine preoperatively and postoperatively at 24 and 48 hours,
 - serum chloride preoperatively and postoperatively at 24 and 48 hours,
 - clinically-determined need for dialysis prior to discharge, and
 - arterial pH, measured 24 hours after surgery.

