- All investigators have available time (non-clinical days, etc) for completion of research-related tasks as part of their routine job duties.
- UNMH already performs many cardiac surgeries per year, and is equipped with the personnel and other resources needed to provide appropriate care for these patients, including both routine care and care for any complications or other unexpected situations.
- All investigators will receive a copy of the HRRC-approved protocol and will participate in discussions about the research plan and logistics.

10. Prior Approvals

10.1. HRRC approval will be obtained before research activities commence.

10.2. The Departmental Review Form is included with this application.

10.3. This study does not involve ionizing radiation.

10.4. This study does not involve the collection of biological specimens for long-term storage. All blood and urine samples obtained will be destroyed as appropriate upon completion of individual lab analyses.

10.5. This study will be listed on ClinicalTrials.gov.

11. Multi-Site Research

11.1. This is not multi-site research.

12. Study Procedures

12.1. Consenting patients will be randomly assigned to receive either Isolyte-S balanced crystalloid or normal saline for intraoperative maintenance and resuscitation fluids. The amount administered is left to the discretion of the clinical providers, according to usual clinical criteria and practice. Other than the product selection of normal saline vs. Isolyte, this study presents no changes to patient treatment.

- Consenting patients will be randomly assigned to receive either Isolyte-S or normal saline solution in the perioperative period, in an amount determined by the provider for clinical reasons. Data to be gathered include basic demographic data, surgery type, and certain laboratory values. Lab data to be gathered include serum creatinine levels preoperatively, as well as levels of TIMP2, IGFBP7, serum creatinine, serum chloride, and arterial pH at timepoints as defined in the primary and secondary outcome measures listed above. The need for dialysis (clinically determined by an attending physician independently of this research study) prior to discharge will also

The Impact of Low Chloride Containing Fluids on Acute Kidney Injury after Cardiopulmonary Bypass as Assayed by Urinary [TIMP2]*[IGFBP7]

- be recorded. The outcome measures are intended to indicate risk for or actual acute kidney injury.

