- Both normal saline and Isolyte-S (B Braun Medical Inc., Bethlehem PA, USA) are legally marketed in the United States, and FDA approved for this indication (fluid maintenance). Providers already have clinical discretion to administer either normal saline or Isolyte-S in the setting of cardiac surgery, and it is normal practice to administer electrolyte-containing fluids intravenously during these surgeries.
 - Subjects will not be asked to complete a questionnaire or otherwise volunteer information.
 - All study data will be sourced from patient medical records, except for the TIMP2 and IGFBP7 laboratory values.
 - The preoperative serum creatinine test is part of routine practice, and is expected for all preoperative cardiac surgery patients. Intraoperative fluid maintenance is routine for surgical patients, and providers already have clinical discretion to administer normal saline or Isolyte-S. Arterial blood pH monitoring is also routine for these patients. The remaining data consists of laboratory values. Routine labwork (including all of the lab-based secondary outcome measures) is an expected part of cardiac surgery patients' postoperative care. The TIMP2*IGFBP7 index will be obtained in addition to routine postoperative monitoring; routine postoperative labwork (e.g. to assess kidney function) is not being replaced.
 - This is not a humanitarian-use device study.
 - There will be an interim review of all study data after completion of the 20th participant, in an effort to detect any unusual patterns of morbidity/mortality. All outcomes will be analyzed. The study will be suspended if this interim review detects a statistically-significant difference is detected between study arms with respect to the clinically-determined need for dialysis prior to discharge.

13.Data Analysis

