- 13.1. The primary outcome involves a composite index: the product of urinary TIMP2 and IGFBP7 values. For a given patient, this index will be calculated for preoperative values and for postoperative values as described above, and the difference between pre- and postoperative index values will be recorded as the primary outcome. A t-test (or Wilcoxon-Mann-Whitney test, in the case of nonnormal distributions) will be used to evaluate the hypothesis. Secondary outcomes that similarly involve pre- vs. postoperative changes in laboratory values (serum creatinine and serum chloride) will be tested in the same fashion. The 24-hour arterial pH data will be assessed with t-test or Wilcoxon-Mann-Whitney as appropriate depending on distribution normality. The clinically-determined need for dialysis prior to discharge will be assessed with Fisher's Exact test.
- 13.2. A power analysis with G*Power 3.1.9.2 software indicates that this sample size is sufficient in the context of a t-test to detect a difference between groups for the primary outcome that is roughly equal to the sample standard deviation. For (purely hypothetical) example, if the mean is 100 units and roughly 2/3 of the sample falls between 95 and 105, we would have 80% power to detect a treatment difference of 5 units.

14. Provisions to Monitor the Data to Ensure the Safety of Subjects

- 14.1. Both normal saline and Isolyte have been used routinely in cardiac procedures for many years, nationally and at UNMHSC, and both have excellent safety records. The PI [name] and co-investigators will conduct an interim review of patient records upon completion of data collection for the 20th participant, in an effort to detect substantial differences in outcomes.
- 14.2. All study data will be reviewed.
- 14.3. Both normal saline and Isolyte have been safely used in cardiac surgery for many years. It is exceedingly unlikely that scientific literature would indicate a substantial difference in risk posed by these two solutions; however, as Chief of Cardiac Anesthesia at UNMH, [name] routinely reviews scientific/medical literature related to cardiac surgery.
- 14.4. Patient records will be reviewed for unusual patterns of morbidity/mortality. In addition, all outcomes will be analyzed with the above-described statistical tests.

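### The only acid-base outcome is one 24-hour arterial pH, which cannot separate metabolic from respiratory change; base excess or bicarbonate from the same gas would be more sensitive

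*Combined protocol and SAP*

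**What the plan says.** The Background (2.1) lists, among the effects of excess chloride in animal models, a "hyperchloremic metabolic acidosis, increased renal vascular resistance" and reduced renal blood flow and filtration.

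Section 7.1 gives one acid-base outcome, the last of four secondary outcomes: "arterial pH, measured 24 hours after surgery". Chloride, by contrast, is taken as "serum chloride preoperatively and postoperatively at 24 and 48 hours", creatinine has the same schedule, and the primary index is a change from baseline. So pH is the only laboratory outcome without a preoperative value.

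Section 12.1 describes collection in general terms ("Data to be gathered include basic demographic data, surgery type, and certain laboratory values") and then limits the laboratory items to the biomarkers, creatinine, "serum chloride, and arterial pH at timepoints as defined in the primary and secondary outcome measures listed above". PaCO2, bicarbonate, base excess and ventilation data appear nowhere as data items. Section 6.1 says other data are gathered around surgery but does not name pH. Section 12.1 also notes: "Arterial blood pH monitoring is also routine for these patients".

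The analysis in 13.1 is: "The 24-hour arterial pH data will be assessed with t-test or Wilcoxon-Mann-Whitney as appropriate depending on distribution normality". Section 3.1 says the investigators "will similarly analyze routine demographic data and potential confounders, as well as secondary outcomes as listed below", but it names no confounder and gives no adjusted model.

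**The concern.** The effect named in 2.1 is metabolic, and the outcome in 7.1 is not specifically metabolic. Arterial pH is fixed by the ratio of bicarbonate to PaCO2. A patient whose bicarbonate has fallen but whose PaCO2 has fallen in proportion has a normal pH. A patient with normal bicarbonate and a raised PaCO2 has a low one. In the first day after cardiac surgery PaCO2 can plausibly vary for reasons unrelated to the study fluid.

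What is at stake is the reading of one secondary outcome. A null pH result could be reported as no acid-base difference between the fluids when a metabolic difference was present. A positive result could not be attributed to a metabolic change. With PaCO2 and base excess uncollected, neither question could be answered afterwards.

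**Working it through.** **The plan's own figure.** The only power statement (5.3, repeated in 13.2) is 80% for a difference of about one SD in the primary outcome with 30 patients. With 15 per arm and an assumed two-sided 5% level (the plan states neither level nor sidedness), the normal approximation gives 78.2% and the noncentral t gives 75.3%. One-sided, the noncentral t gives 84.8%. That is close to the stated figure and has no bearing on pH, for which the plan gives no power or precision.

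**Why pH alone is ambiguous.** From the Henderson-Hasselbalch relation, pH = 6.1 + log10[HCO3 / (0.03 × PaCO2)], with illustrative values not taken from the documents:

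| HCO3 (mmol/L) | PaCO2 (mmHg) | pH |
|---|---|---|
| 24 | 40 | 7.401 |
| 21 | 35 | 7.401 |
| 21 | 40 | 7.343 |
| 24 | 46 | 7.340 |

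Rows 1 and 2 show a 3 mmol/L metabolic deficit that pH does not register. Rows 3 and 4 show a metabolic and a respiratory disturbance with nearly the same pH.

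**What this does to sensitivity.** Only the 15 per arm comes from the plan (5.2). The bicarbonate means and SDs, the PaCO2 mean of 40 mmHg and its SD are all assumptions. Bicarbonate and PaCO2 are first taken as independent.

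- On bicarbonate, the standardised difference is d = difference / SD.
- On pH, the mean difference is log10(mean HCO3 in arm 1 / mean HCO3 in arm 2). Its SD is approximately 0.4343 × √[(SD of HCO3 / average HCO3)² + (SD of PaCO2 / 40)²].

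For 24 against 22 mmol/L, SD 2, PaCO2 SD 5:

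- Bicarbonate: d = 2/2 = 1, power 75.3%.
- pH difference: log10(24/22) = 0.0378.
- pH SD: 0.4343 × √[(2/23)² + (5/40)²] = 0.0661.
- pH: d = 0.0378/0.0661 = 0.571, power 32.7%.

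The same steps, all with PaCO2 SD 5, give:

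| Difference, bicarbonate SD | d on bicarbonate | Power | d on pH | Power |
|---|---|---|---|---|
| 2, SD 2 | 1.00 | 75.3% | 0.571 | 32.7% |
| 2, SD 3 | 0.667 | 42.2% | 0.482 | 24.7% |
| 1, SD 2 | 0.50 | 26.2% | 0.281 | 11.6% |

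Simulating the exact relation gives pH powers within one percentage point of these. Rounded, the pH figures are about 32%, 25% and 11%. In the first scenario, simulated pH power is about 51% at PaCO2 SD 3 and 26% at SD 6, against 75% on bicarbonate throughout.

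**Compensation.** Independence favours pH. If PaCO2 falls by 0.5 to 1.2 mmHg per mmol/L fall in bicarbonate (assumed), simulated pH power in the first scenario falls to between 39% and 13% at residual PaCO2 SD 3, and to between 21% and 8% at SD 5. This shrinks the pH difference itself as well as blurring it.

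**The case against.** Four points on the other side have weight.

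- **The trial is not about acidosis.** A reader might infer that the pH outcome tests the trial's central mechanism. The documents do not support that. The objective (1.1) and primary outcome (7.1) are kidney injury by urinary biomarker, and 12.1 describes the outcomes as indicators of kidney injury or its risk. Section 2.1 lists acidosis beside the renal haemodynamic effects without saying that these act through it. No mediation analysis is planned. This stands.
- **Randomisation protects the comparison.** A reader might infer that ventilation biases the pH result. Allocation is 1:1 at random (3.1), so baseline pH and unrelated PaCO2 variation are balanced in expectation, and 13.1 estimates the effect on pH without bias from that source. This stands. It does not remove the extra variance. Nor does it balance compensation, which follows from the treatment effect.
- **The missing preoperative pH is no error.** It biases nothing, and 13.1 treats pH as a post-treatment value, consistent with 7.1. The cost is precision at most. The documents do not say that a gas is routinely drawn before study fluid, so a required baseline could reduce the analysed number. This stands.
- **The power figures rest on no document input.** That is true, and the 75% figure belongs to a favourable scenario. In the other two scenarios neither measure is adequately powered. The ordering does not change: bicarbonate does better in every case tried.

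Serum chloride before surgery and at 24 and 48 hours covers exposure to chloride, but not its acid-base consequence.

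**Conclusion.** The point holds as one of sensitivity and interpretation in a single secondary outcome. A lone 24-hour pH is a weak and ambiguous measure of the metabolic effect named in 2.1, and a metabolic measure would be better. In the three scenarios shown at PaCO2 SD 5, power on pH is between roughly two fifths and three fifths of that on bicarbonate (11/26 = 0.42, 32/75 = 0.43, 25/42 = 0.60). The loss is smaller if PaCO2 varies less and larger with respiratory compensation. These ratios rest wholly on assumed means and SDs and show direction and rough scale only.

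The primary outcome, the sample size, the interim rule and the main conclusion are unaffected. The documents support neither a claim of bias nor a claim that the absent baseline invalidates the pH comparison.

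**What to change.** - **7.1 and 12.1:** add base excess (or bicarbonate) and PaCO2, abstracted from the same 24-hour arterial gas report that supplies the pH. Choose base excess or bicarbonate in advance.
- **13.1:** make that measure the acid-base comparison between arms, with the tests already planned, and report pH and PaCO2 as supporting values.
- **Optional:** where a routine arterial gas before study fluid exists, abstract it and use it only for a supportive baseline-adjusted analysis. Patients without one stay in the main comparison.

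The cost is a few more abstracted fields and a reworded secondary outcome, with no change in sample size or care. No extra sample is needed provided the routine report carries these values. That is an assumption, since 12.1 mentions only pH monitoring, and it should be confirmed with the hospital laboratory.

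The change should be made before data collection ends. Section 16.6 has forms with identifiers shredded once deidentified data are entered, after which the missing values could not be linked back to patients.

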Historically, one of the most common balanced salt-solutions used in adult cardiac surgery has been 0.9% normal saline (NS), a crystalloid solution with 154 mmol/L of Cl⁻. This is much higher than physiologic plasma levels of 103 mmol/L. Isolyte, a less commonly used crystalloid solution, is much closer to physiologic levels at 98 mmol/L Cl⁻. In the context of cardiac surgery, **there is no literature** expressly comparing the effects of balanced crystalloid solution such as Isolyte versus NS on AKI incidence. There is a single trial examining a low-Cl⁻ containing colloid solution in cardiac surgery that found less metabolic acidosis[15]; however, AKI or markers of AKI were not measured outcomes in that lone trial, so **it is not known whether low Cl⁻ solution will have any effect on AKI risk in humans.**

AKI results from a series of extremely complex cellular and molecular pathways involving endothelial, epithelial, inflammatory, and interstitial cells. The gold standard for identification and classification of AKI is dependent on serial serum creatinine (Scr) measurements[16], but this measurement can be unreliable during acute changes in kidney function.[17, 18] Recent studies have shown that tissue inhibitor of metalloproteinase (TIMP-2) performs better than existing markers for predicting the development of moderate or severe AKI (KDIGO stage 2 or 3) within 12 hours of sample collection.[19] To further enhance the sensitivity of utilizing TIMP-2, we plan on also measuring urinary insulin-like growth factor-binding protein 7 (IGFBP7). Along

The Impact of Low Chloride Containing Fluids on Acute Kidney Injury after Cardiopulmonary Bypass as Assayed by Urinary [TIMP2]*[IGFBP7]

with TIMP-2, IGFBP7 is also an inducer of G1 cell cycle arrest, a key mechanism implicated in AKI.[19]

This study will utilize the urinary [TIMP-2]*[IGFBP7] multiplicative product as a composite biomarker index to investigate the impact of intraoperative infusion of NS versus Isolyte on post-cardiac surgery renal function. This biomarker should identify patients at risk of imminent (within 12 hours) AKI according to the Kidney Disease: Improving Global Outcomes (KDIGO) criteria.[19, 20].

- 2.2. The investigators have not gathered preliminary data.

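### The planned two-group test on the change is valid, but it uses the preoperative index only by subtraction; adding that index as a covariate in both branches of the test would usually gain precision at almost no cost.

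*Combined protocol and SAP*

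**What the plan says.** Section 7.1 defines the endpoint: "The primary outcome is the change in urinary [TIMP2]*[IGFBP7] composite from baseline to 24 hours postoperatively". Section 13.1 computes the index before and after surgery, and "the difference between pre- and postoperative index values will be recorded as the primary outcome". The test follows: "A t-test (or Wilcoxon-Mann-Whitney test, in the case of nonnormal distributions) will be used to evaluate the hypothesis". Changes in the two laboratory secondaries are handled alike ("serum creatinine and serum chloride) will be tested in the same fashion").

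No covariate appears in any analysis. Nothing says how nonnormality is to be judged: no test, no cut-off, and no statement of whether arms are examined separately or pooled. Section 3.1 calls the tests pairwise, whereas 5.3 and 13.2 speak of a difference between groups.

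On precision, 5.2 plans 15 complete patients per arm. Sections 5.3 and 13.2 claim 80% power "to detect a difference between groups for the primary outcome that is roughly equal to the sample standard deviation", without stating alpha or sidedness. Section 2.2 adds: "The investigators have not gathered preliminary data".

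**The concern.** A change score removes the baseline with a fixed coefficient of 1. If the true slope of the 24-hour index on the preoperative index is well below 1, subtraction puts baseline noise into the outcome. A model with the preoperative index as covariate estimates the slope instead. With 15 per arm and power only for an effect of about 1 SD, precision is the scarce resource, and the baseline is collected anyway.

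The second issue is specification. Observed normality chooses between a mean comparison and a rank comparison with no written criterion. The trial is open-label (3.2), "co-investigators will conduct an interim review of patient records upon completion of data collection for the 20th participant", and 14.4 has all outcomes analysed at that review. A choice left open would therefore be made by people who may already have seen results by arm.

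**Working it through.** **Inputs from the documents.** 15 per arm (5.2); outcome is the change (7.1, 13.1); target effect about 1 SD and power 80% (5.3, 13.2).

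**Assumed, because not given.** Alpha 0.05 two-sided; correlation ρ between pre and post of 0.3, 0.5 or 0.7; ratio k of postoperative to preoperative SD of 1, 1.5 or 2; normal or lognormal data. Where a normality rule is needed, Shapiro-Wilk at 0.05 in each arm.

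**Step 1: the plan's own figure.** For a difference of 1 SD of the change, the noncentrality is √(15/2) = 2.739.
- Normal approximation, two-sided 0.05: 78.2%.
- Noncentral t, 28 df: 75.3% two-sided, 84.8% one-sided.
- Exact 80% two-sided is reached at 1.06 SD.

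The plan says only roughly 1 SD, so its 80% is reproduced within its own tolerance.

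**Step 2: validity.** With no treatment effect, simulated rejection rates at 15 per arm were 3.5–5.1% for the t-test, 4.1–4.8% for Wilcoxon and 4.6–5.3% for the Shapiro-Wilk-gated choice. Taking the smaller of the two p-values, the worst use of an open choice, gave 5.2–6.1%.

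**Step 3: gain from adjustment, normal data.** With preoperative variance set to 1:
- variance of the change = 1 + k² − 2ρk
- residual variance given baseline = k²(1 − ρ²)
- ratio R = k²(1 − ρ²) / (1 + k² − 2ρk)
- true slope = ρk

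For k = 1, R = (1 + ρ)/2, which is 0.65, 0.75 and 0.85. For k = 2 and ρ = 0.5, R = 4 × 0.75 / (5 − 2) = 1: the slope is exactly 1 and there is nothing to gain.

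Adjusted power is noncentral t with 27 df and noncentrality 2.739/√(R·V). V = 1 + F(1,28)/28 allows for chance baseline imbalance, and power is averaged over it. The unadjusted comparator is 75.3% throughout.

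| k | ρ = 0.3 | ρ = 0.5 | ρ = 0.7 |
|---|---|---|---|
| 1 | 89.5% | 84.9% | 80.3% |
| 1.5 | 79.3% | 75.2% | 73.7% |
| 2 | 75.4% | 73.6% | 76.8% |

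Five of the nine cells gain 1.5 points or more (up to 89.5 − 75.3 = 14.2), two are within 0.1 point of no change, and two lose 75.3 − 73.7 = 1.6 and 75.3 − 73.6 = 1.7.

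**Step 4: why the nonnormal branch needs its own adjusted form.** Take lognormal data with log-SD 1, ρ = 0.5, a postoperative rise of 1 log unit and an effect of −1 / +1 log-SD. The plan's gated rule has 73.5% / 79.5% power. A linear adjusted model on the untransformed index, used whatever the skew, has 61.6% / 61.4%, so it loses 11.9 and 18.1 points. The rank fallback in 13.1 is doing useful work and should be kept, with the baseline added.

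**Step 5: baseline added to both branches.** The model is linear if the change passes the criterion; otherwise the rank of the change is fitted on arm and rank of the preoperative index. Compared with the plan's rule over 15 simulated non-null settings:
- lognormal settings: 0 to 28 points more power
- settings where pre and post shapes differ: about 2 points less to 7 points more
- largest loss in any setting: about 2 points
- type I error: 5.0% (normal) and 5.8% (lognormal, where the plan's rule gave 5.3%)

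**The case against.** The strongest reply is that nothing here is an error. A two-group test of a prespecified change is legitimate and holds its level, every gain rests on assumed inputs, and some plausible inputs give no gain. All of that stands. It makes this a recommendation and not a correction.

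Three stronger readings are tempting, and none is supported.

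- *The power claim is wrong, because the exact two-sided figure at 1 SD is 75.3%.* Alpha and sidedness are not stated, and the plan's approximate wording covers 1.06 SD.
- *The missing normality criterion decides the trial's power.* In the skewed setting of Step 4, Wilcoxon has 73.9% / 79.3% against 59.8% / 61.4% for the t-test. But the plan's rule, read as a Shapiro-Wilk gate, has 73.5% / 79.5%, so it already captures that advantage. Only a criterion blind to strong skew would lose it. The criterion should be written down, but that is tidiness more than rescue.
- *The scale should be chosen by a rule on the preoperative values, for example log if their pooled skewness exceeds 0.5.* This does well when pre and post values share a shape and the effect is multiplicative, but nothing in the documents says they do. With a skewed baseline (log-SD 1) and a normal additive change, such a rule has 48% power against 76% for the plan. With a normal baseline and lognormal postoperative values (log-SD 1), it has 64–65% against 75–77%. It also leaves the data to decide whether the effect is a difference or a ratio.

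**Conclusion.** The point holds as one of efficiency and specification. The planned analysis is valid. It discards information in the preoperative index unless the true pre/post slope happens to be near 1.

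Under normal data with equal SDs, adjustment is worth about 14, 10 and 5 power points at correlation 0.3, 0.5 and 0.7. With a postoperative SD 1.5 to 2 times baseline, it ranges from a gain of 4 points to a loss of about 2. Under skew, the gain depends on keeping a rank branch. All of these figures assume 15 per arm and two-sided 0.05, with correlations, SD ratios and shapes that the documents do not supply. The simulated figures also assume a Shapiro-Wilk criterion. A reader should take the direction and the small downside as the finding, not any single percentage.

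**What to change.** In 13.1, keep the change as the outcome and replace the test sentence with text to this effect:

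*The primary analysis is a linear model of the change in the index (24 hours minus preoperative) on study arm, with the preoperative index as covariate, reported as the adjusted difference between arms with 95% CI. If the change is nonnormal (Shapiro-Wilk p < 0.05 in either arm), the rank of the change is modelled on study arm and the rank of the preoperative index, in place of Wilcoxon-Mann-Whitney.*

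Shapiro-Wilk is an example. What matters is that one criterion is written before any outcome is seen. Treat the creatinine and chloride changes in the same way. In 3.1, replace the reference to pairwise tests with the between-group analysis of 13.1, because a within-patient paired test would not compare the arms.

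Do not adopt a linear model on the untransformed index regardless of skew, or a raw-or-log choice driven by preoperative skewness.

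Cost: one residual degree of freedom, wording in 13.1 and 3.1, no new data or visits, and at most about 2 power points in the settings tried. Like Wilcoxon, the rank branch gives a test and not an estimate in index units.
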